6.3.6. Analysis of immunogenicity by Frailty status

The analysis of immunogenicity will be categorised by vaccination group and frailty status. The primary analysis will be based on the ATP cohort for analysis of immunogenicity – ZOSTER064.

6.3.6.1. Cell-mediated immune response

Cell-mediated immune response will be assessed and analysed in the ATP cohort for analysis of immunogenicity – CMI.

FORM-9000026972-01 Statistical Analysis Plan Template Effective date: 01 Sep 2015

Study alias & e-track number(s): ZOSTER-064 (204878)

The CMI analyses was performed for ZOSTER-006 only in the Immunogenicity subset in three countries (Czech Republic, Japan and United States) at designated sites that had access to a PBMC processing facility within the acceptable time window from sample collection to PBMC processing. The CMI subset contained approximately 350 subjects. We are expecting some attrition of data, i.e. some centres who took part in the ZOSTER-006 may not take part in the ZOSTER-064. In addition, we are expecting that approximately 5% of subjects will be classified as frail. As a consequence, the analysis of CMI by frailty status will only be carried out if we have a minimum of 20 CMI subjects classified as frail.

6.3.6.2. Descriptive statistics

For CMI response, the following parameters (for gE and VZV specific CD4[2+] frequency and CD4[+2] T-cell following induction with gE and VZV) will be tabulated by vaccination group, overall and by frailty status at Months 0, 3, 14, 26 and 38:

- descriptive statistics of the frequency of CD4 T-cell secreting at least two different cytokines (IFN-γ, IL-2, TNF-α, CD40L) to both VZV and gE antigens;
- descriptive statistics of the frequency of CD4 T-cell secreting at least IFN-γ and another cytokine (IL-2, TNF-α, CD40L) to both VZV and gE antigens;
- descriptive statistics of the frequency of CD4 T-cell secreting at least IL-2 and another cytokine (IFN-γ, TNF-α, CD40L) to both VZV and gE antigens;
- descriptive statistics of the frequency of CD4 T-cell secreting at least TNF-α and another cytokine (IFN-γ, IL-2, CD40L) to both VZV and gE antigens;
- descriptive statistics of the frequency of CD4 T-cell secreting at least CD40L and another cytokine (IFN-γ, IL-2, TNF-α) to both VZV and gE antigens;
- Vaccine response rate with exact 95% CI at Months 3, 14, 26 and 38 (only in the gE-specific CD4[2+] T-cell frequency at Months 3, 14, 26 and 38)

6.3.6.3. Inferential Analyses

No inferential analysis will be carried out on the CMI data.

6.3.6.4. Humoral immune response

Humoral immune response will be assessed and analysed in the ATP cohort for analysis of immunogenicity – Humoral.

FORM-9000026972-01 Statistical Analysis Plan Template Effective date: 01 Sep 2015

Study alias & e-track number(s): ZOSTER-064 (204878)

6.3.6.5. Descriptive statistics

For the humoral immune response, at each timepoint that a blood sample is available (Months 0, 3, 14, 26 and 38), the following parameters (with 95% CIs) will be tabulated by vaccination group and frailty status:

- Geometric mean concentrations (GMCs) of anti-gE Ab with 95% confidence interval (CIs);
- Humoral seropositivity rates with exact 95% confidence interval (CIs);
- Vaccine response rates with 95% confidence interval (CIs);

6.3.6.6. Inferential Analyses

No inferential analysis will be carried out on the humoral immune response data.

7. STATISTICAL CALCULATIONS

7.1. Derived and transformed data

7.1.1. Demography

Age at vaccination

Age will be calculated as the number of years between the date of birth and the date of first vaccination.

To ensure that the collection of date of birth will not jeopardise the privacy of Personally Identifiable Information (PII), only a partial date of birth (MMYYYY) was collected.

Therefore, the 15th of the month will be used to replace the missing date.

In case the month is missing, the date will be replaced by the June 30th of the year.

Note that due to incomplete date, the derived age may be incorrect by 1 month when month is missing from the birthdate. This may lead to apparent inconsistency between the derived age and the eligibility criteria/the age category used for randomization.

FORM-9000026972-01 Statistical Analysis Plan Template Effective date: 01 Sep 2015

Study alias & e-track number(s): ZOSTER-064 (204878)

7.1.2. Efficacy data

Details of derived and transformed efficacy data including the methodology behind the VE is contained in the SAPs for the ZOSTER-006 and ZOSTER-022 studies.

7.1.3. Safety

Details of derived and transformed safety data is contained in the SAPs for the ZOSTER-006 and ZOSTER-022 studies.

7.1.4. Immunogenicity

7.1.4.1. Humoral immune response

Full details of the methods used in the humoral immune response analyses are contained in the ZOSTER-006 and ZOSTER-022 SAPs (Demog, Safety, Immuno)

7.1.4.2. Cellular-mediated immune (CMI) response

Full details of the methods used in the CMI analysis including calculation of the frequency of antigen-specific (gE or VZV) CD4[2+] T cells for each individual subject and the definition of CMI vaccine response to gE and VZV are contained in the ZOSTER-006 SAP (Demog, Safety, Immuno)

7.2. Quality of Life data

7.2.1. SF-36 and EQ-5D

Details of the derivation of the 8 scales generated from the SF-36 and the derivation of the utility score from the EQ-5D are contained in the quality of life (QoL) SAPs for the ZOSTER-006 and ZOSTER-022 studies.

7.2.2. HZ Burden of illness

The HZ burden of illness scores are based on the ZBPI questionnaire already encoded in the ZOSTER-006 and ZOSTER-022 studies.

Full details of the ZBPI questionnaire and the methodology behind the calculation of the HZ burden of illness scores are contained in the statistical analysis plans (QoL) for the ZOSTER-006 and ZOSTER-022 studies.

FORM-9000026972-01 Statistical Analysis Plan Template Effective date: 01 Sep 2015

GSK SOP Reference: SOP-9000026972 Form Owner: VVHS Biometrics, PPD

Study alias & e-track number(s): ZOSTER-064 (204878)

7.3. Frailty Index

Frailty status will be measured in relation to the accumulation of deficits using a frailty index (FI) adapted from the model proposed by Mitnitski et al. [Mitnitski, 2001]. The different aspects of frailty composing the frailty index will be assessed through the medical history and components of the *SF-36* and *EQ-5D* questionnaires recorded prevaccination Dose 1.

The total frailty score will be between 0 and 41. The subject's pre-vaccination questionnaires will contribute a max score of 29 and the medical history will contribute a max score of 12. Table 3 details the components of the SF-36 and EQ-5D questionnaires that contribute to the calculation of the frailty index.

27-NOV-2018

GSK SOP Reference: SOP-9000026972 Page 22 of 30 Form Owner: VVHS Biometrics, PPD

Study alias & e-track number(s): ZOSTER-064 (204878)

Table 3 Detail of SF-36 and EQ-5D components of frailty Index

Item	Scoring method based on response to question	Max Contribution to Frailty Index
SF-36 Q1	Poor=1,	1
	Fair=0.5	
	Good=0,	
	Very good=0	
	Excellent=0	
SF-36 Q11A-11D	Q11A, Q11C	4
	Definitely true=1	
	Mostly true=0.5	
	Don't know=0	
	Mostly false=0	
	Definitely false=0	
	Q11B, Q11D	
	Definitely true=0	
	Mostly true=0	
	Don't know=0	
	Mostly false=0.5	
	Definitely false=1	
SF-36 Q3I - Q3J	Limited a lot=1	10
	Limited a little=0.5	1
	Not limited at all=0	
SF-36 Q9A - Q9I	Q9A, Q9D, Q9E, Q9H:	9
J. 55 457. 451	All of the Time=0	
	Most of the time=0	
	Some of the time=0	
	A little of the time=0.5	
	None of the time=1	
	Q9B, Q9C, Q9F, Q9G, Q9I :	
	All of the Time=1	
	Most of the time=0.5	
	Some of the time=0	
	A little of the time=0	
	None of the time=0	
SF-36 Q2 Compared to one week	Much worse=1,	1
before, how did the subject rate his / her	Somewhat worse=0.5,	'
health in general?	Same=0	
nediti in general:	Somewhat better=0	
	Better=0	
EQ-5D Mobility	No Problems=0	1
L& OD MODILLY	Some Problems=0.5	Ι'
	Confined to bed=1	
EQ-5D Anxiety	No Anxiety=0	1
LQ-0D Allklety	Moderate Anxiety=0.5	['
EQ-5D Self care	Extreme Anxiety=1 No Problems=0	1
EQ-0D Sell care	Some Problems=0.5	['
	Inability to wash or dress himself	
	/herself=1	
	/IICI 3CII - I	1

FORM-9000026972-01 Statistical Analysis Plan Template

Effective date: 01 Sep 2015

GSK SOP Reference: SOP-9000026972 Form Owner: VVHS Biometrics, PPD

Study alias & e-track number(s): ZOSTER-064 (204878)

Item	Scoring method based on response	Max Contribution to	
	to question	Frailty Index	
EQ-5D Usual activities	No Problems=0	1	
	Some Problems=0.5		
	Inability to perform usual activities=1		
Total		29	

The medical history is divided into 12 categories; each category contributing a score of 0 or 1. The coded combined ZOSTER-006 and ZOSTER-022 medical history database will be searched and events that fall into any one of the 12 categories will be selected Table 4 details the MedDRA terms that will be used to search the database. If a subject had any one of the listed events in a category they would be assigned a max score of 1 for that category and a max score of 12 overall.

The frailty index is then calculated by combining the accumulation of deficits into a score from 0 to 1: frailty index = (accumulation of deficits) / (41 – nmissQoL) where nmissQoL is the number of missing components of the 29 items from the SF-36 and EQ-5D questionnaires. If a subject has more than 10 missing QoL components the frailty index will not be calculated.

Each subject will then be assigned to one of three categories, Non-Frail, Pre-Frail and Frail based on the frailty index.

• If the frailty index is **less than or equal to** 0.08 then the subject is classified as Non-Frail. If the score is greater than 0.08 **but less than or equal to** 0.25 then the subject is classified as pre-frail. If the score is **greater than** 0.25 then the subject is classified as Frail. Subjects without a frailty index score will be classified as missing.

FORM-9000026972-01 Statistical Analysis Plan Template Effective date: 01 Sep 2015

Study alias & e-track number(s): ZOSTER-064 (204878)

Table 4 Detail of Medical history search items

Category	MedDRA version 18 Search Terms
Cancer	Malignancy related conditions (SMQ)
	Malignant tumours (SMQ)
Diabetes Mellitus	Diabetes mellitus (incl subtypes) (HLT)
	Diabetic complications (HLGT)
High Blood Pressure,	Hypertension (SMQ)
Heart Attack	Ischaemic heart disease (SMQ)
CHF	Cardiac failure (SMQ)
Cerebrovascular Disease	Central nervous system vascular disorders (SMQ)
Arthritis	Arthritis (SMQ)
Chronic Lung	Asthma/bronchospasm (SMQ)
Disease	Interstitial lung disease (SMQ)
	Pulmonary hypertension (SMQ)
	Chronic Obstructive Pulmonary Disease (PT) / Infective exacerbation of
	chronic obstructive airways disease (PT)
	Bronchiectasis (PT) /Infective exacerbation of bronchiectasis (PT)
	Cystic fibrosis (PT)/ Cysitic fibrosis lung (PT) / Infective pulmonary
	exacerbation of cystic fibrosis (PT)
	Chronic respiratory disease (PT)
	Chronic respiratory failure (PT)
Stomach or Intestinal Ulcers	Gastrointestinal ulceration (SMQ)
Migraine	Migraine headaches (HLT)
	Migraine prophylaxis (PT)
Cataract	Cataract Conditions (HLT)
	Cataract operation (PT)
	Cataract diabetic (PT)
	Cataract operation complication (PT)
Glaucoma	Glaucoma (SMQ)

 SMQ: Standardised MedDRA queries. HLGT: High Level Group Term. HLT: High Level Term. PT: Preferred Term

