10.7.4. Definition of Frailty

Frailty status will be measured in relation to the accumulation of deficits using a frailty index (FI) adapted from the model proposed by Mitnitski et al. [Mitnitski, 2001]. The different aspects of frailty composing the FI will be assessed through the medical history and *SF-36* and *EQ-5D* questionnaires recorded pre-vaccination dose 1. The frailty index will be a score between 0 and 41 as detailed in Table 3.

Table 3 Detail of frailty components

Item	Scoring method based on response to question	Max Contribution to Frailty Index
SF-36 Q1	Poor=1, Fair=0.5 Good=0, Very good=0 Excellent=0	1
SF-36 Q11A-11D	Q11A, Q11C Definitely true=1 Mostly true=0.5 Don't know=0 Mostly false=0 Definitely false=0	4

CONFIDENTIAL

204878 (ZOSTER-064)
Protocol Administrative Change 3 Final

Item	Scoring method based on response to question	Max Contribution to Frailty Index
	Q11B, Q11D Definitely true=0 Mostly true=0 Don't know=0 Mostly false=0.5 Definitely false=1	
SF-36 Q3I - Q3J	Limited a lot=1 Limited a little=0.5 Not limited at all=0	10
SF-36 Q9A - Q9I	Q9A, Q9D, Q9E, Q9H: All of the Time=0 Most of the time=0 Some of the time=0 A little of the time=0.5 None of the time=1 Q9B, Q9C, Q9F, Q9G, Q9I : All of the Time=1 Most of the time=0.5 Some of the time=0 A little of the time=0 None of the time=0	9
SF-36 Q2 Compared to one week before, how did the subject rate his / her health in general?	Much worse=1, Somewhat worse=0.5, Same=0 Somewhat better=0 Better=0	1
EQ-5D Mobility	No Problems=0 Some Problems=0.5 Confined to bed=1	1
EQ-5D Anxiety	No Anxiety=0 Moderate Anxiety=0.5 Extreme Anxiety=1	1
EQ-5D Self care	No Problems=0 Some Problems=0.5 Inability to wash or dress himself /herself=1	1
EQ-5D Usual activities	No Problems=0 Some Problems=0.5 Inability to perform usual activities=1	1
Medical history	Cancer	1
	Diabetes Mellitus	1
	High Blood Pressure	1
	Heart Attack	1
	Congestive Heart Failure	1
	Cerebrovascular Disease	1
	Arthritis	1
	Chronic Lung Disease	1
	Stomach or Intestinal Ulcers	1
	Migraine	1
	Cataract	1
Glaucoma	1	
Total		41

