The medical history is divided into 12 selected categories; each category contributing a score of 0 or 1. The coded combined ZOSTER-006 and ZOSTER-022 medical history database will be searched and events that fall into any one of the 12 categories will be selected Table 4 details the MedDRA terms that will be used to search the database. If a subject had any one of the listed events in a category they would be assigned a max score of 1 for that category and a max score of 12 overall.

The frailty index is then calculated by combining the accumulation of deficits into a score from 0 to 1: frailty index = (accumulation of deficits) / (41 – nmissQoL) where nmissQoL is the number of missing components of the 29 items from the SF-36 and EQ-5D questionnaires. If a subject has more than 10 missing QoL components the frailty index will not be calculated.

Each subject will then be assigned to one of three categories, Non-Frail, Pre-Frail and Frail based on the frailty index.

• If the frailty index is **less than or equal to** 0.08 then the subject is classified as Non-Frail. If the score is greater than 0.08 **but less than or equal to** 0.25 then the subject is classified as pre-frail. If the score is **greater than** 0.25 then the subject is classified as Frail. Subjects without a frailty index score will be classified as missing.

Table 4 Detail of Medical history search items

2 (W IDDA ' 400 I T
Category	MedDRA version 18 Search Terms
Cancer	Malignancy related conditions (SMQ)
	Malignant tumours (SMQ)
Diabetes Mellitus	Diabetes mellitus (incl subtypes) (HLT)
	Diabetic complications (HLGT)
High Blood Pressure,	Hypertension (SMQ)
Heart Attack	Ischaemic heart disease (SMQ)
CHF	Cardiac failure (SMQ)
Cerebrovascular	Central nervous system vascular disorders (SMQ)
Disease	
Arthritis	Arthritis (SMQ)
Chronic Lung Disease	Asthma/bronchospasm (SMQ)
•	Interstitial lung disease (SMQ)
	Pulmonary hypertension (SMQ)
	Chronic Obstructive Pulmonary Disease (PT) / Infective exacerbation of chronic
	obstructive airways disease (PT)
	Bronchiectasis (PT) /Infective exacerbation of bronchiectasis (PT)
	Cystic fibrosis (PT)/ Cysitic fibrosis lung (PT) / Infective pulmonary exacerbation of
	cystic fibrosis (PT)
	Chronic respiratory disease (PT)
	Chronic respiratory failure (PT)
Stomach or Intestinal	Gastrointestinal ulceration (SMQ)
Ulcers	,
Migraine	Migraine headaches (HLT)
· ·	Migraine prophylaxis (PT)
Cataract	Cataract Conditions (HLT)
	Cataract operation (PT)

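### The fixed search list for the Chronic Lung Disease deficit names neither emphysema nor chronic bronchitis; confirm that they are captured, or add them

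*SAP*

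**What the plan says.** Table 3 in Protocol section 10.7.4 allots one point to "Chronic Lung Disease" among 12 medical-history categories. The same section says that the coded history will be searched for relevant preferred terms, and it leaves the details of the index to the SAP.

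Table 4 in section 7.3 of SAP Amendment 1 supplies the terms, under MedDRA version 18. The lung row contains:

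- three standardised queries (SMQs): asthma/bronchospasm, interstitial lung disease and pulmonary hypertension;
- COPD and its infective exacerbation as preferred terms: "Chronic Obstructive Pulmonary Disease (PT) / Infective exacerbation of", with the rest of the second term following;
- preferred terms for bronchiectasis and cystic fibrosis with their infective exacerbations, chronic respiratory disease, and chronic respiratory failure.

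The scoring rule is: "If a subject had any one of the listed events in a category they would be assigned a max score of 1 for that category". The denominator is 41 less the number of missing questionnaire items, and no index is calculated when more than 10 are missing. The superseded SAP of 27 November 2018 carries the same list.

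**The concern.** Table 4 is presented as the search itself, not as a set of examples, and section 7.3 describes no medical review of history terms that the search leaves behind. The lung row reads as if preferred terms are matched exactly: infective exacerbations of COPD, bronchiectasis and cystic fibrosis are each listed beside the parent disease, which would be needless if one term brought in its relatives. Every other category in Table 4 has at least one query or higher-level group term for its named condition. In the lung row, nothing but the asthma/bronchospasm query could group other airway disease. Emphysema and chronic bronchitis are chronic lung diseases, and neither is named.

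A miss would count as health. The denominator shrinks only for missing questionnaire items, so an uncaptured disease leaves a 0 with its place in the denominator kept.

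Frailty status is the primary endpoint (SAP 4.1). It also defines the groups for vaccine efficacy, burden of illness, safety and immunogenicity (SAP 6.3.2, 6.3.3, 6.3.5, 6.3.6). Protocol section 1.2 uses the proportions pre-frail and frail to judge how representative the trial population is. SAP 6.3.6.2 expects only about 5% to be frail, so that group is small.

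**Working it through.** **The plan's own total.** Maximum contributions in SAP Table 3: 1 + 4 + 10 + 9 + 1 + 1 + 1 + 1 + 1 = 29. Adding 12 medical-history categories gives 41, as stated.

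**Inputs.** The cut-offs are 0.08 and 0.25, with equality falling in the lower category (Protocol 10.7.4, SAP 7.3). The denominator is 41 with complete questionnaires and 31 with 10 items missing. Questionnaire items score 0, 0.5 or 1 and history categories 0 or 1, so totals move in steps of 0.5.

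**Cut-offs in points, complete questionnaires.** 0.08 × 41 = 3.28 and 0.25 × 41 = 10.25. Non-Frail is therefore 3.0 or less, Pre-Frail 3.5 to 10.0, and Frail 10.5 or more.

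**Effect of losing one point.** The index falls by 1/41 = 0.024.

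- True 4.0: 4.0/41 = 0.098 (Pre-Frail) is counted as 3.0/41 = 0.073 (Non-Frail). True 3.5 also crosses.
- True 4.5 is counted as 3.5/41 = 0.085 and stays Pre-Frail.
- True 11.0: 11.0/41 = 0.268 (Frail) is counted as 10.0/41 = 0.244 (Pre-Frail). True 10.5 also crosses.
- True 11.5 is counted as 10.5/41 = 0.256 and stays Frail.

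No other total changes category. With missing items the pattern is the same, two half-point totals above each cut-off:

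| Missing items | Denominator | One point | Cut-offs in points | Totals crossing, lower cut-off | Totals crossing, upper cut-off |
|---|---|---|---|---|---|
| 0 | 41 | 0.024 | 3.28; 10.25 | 3.5, 4.0 | 10.5, 11.0 |
| 5 | 36 | 0.028 | 2.88; 9.00 | 3.0, 3.5 | 9.5, 10.0 |
| 10 | 31 | 0.032 | 2.48; 7.75 | 2.5, 3.0 | 8.0, 8.5 |

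**How many subjects.** The share reclassified is a × b, where a is the share of subjects whose lung history is missed and b is the share of those with a total in a crossing band. The documents give neither. As an illustration on assumed inputs only, a = 0.5% with b = 5% gives 0.025% of subjects, and a = 5% with b = 30% gives 1.5%. If the terms are already captured, a = 0 and so is the effect. I do not convert this to a headcount. The pooled figure of 29,305 stands in the superseded SAP (section 5.1) and counts the parent-study cohort, whereas the current cohort drops centres that do not take part in ZOSTER-064.

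**The case against.** The strongest reply is that no miss has been shown. A subject loses the point only if three things hold: the disease was coded to its own preferred term, that term lies outside all three listed queries in MedDRA version 18, and the subject has no other listed lung term. The documents give neither the members of the queries nor the coding in the parent studies, and the title of a query does not settle its contents. This stands, and it is why the point is conditional.

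A reader might go further than the documents allow in three ways.

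- **That the SAP narrows the protocol and should say so in section 9.** The protocol gives only a category name and hands the detail to the SAP, so there is no wider list to narrow. The Protocol Amendment 1 rationale also ties the condition list to the terminology of another study, which is not available here.
- **That frail and pre-frail prevalence is understated overall.** Missing terms can only lower this one item, but other searches may be generous. Heart Attack, for example, is searched with the whole ischaemic heart disease query. The net direction for the index is not shown.
- **That vaccine is favoured over placebo, or the reverse.** The list is applied to baseline history in the same way in both groups.

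It is also fair to say that this is one item of 41, in analyses that the protocol calls exploratory (10.7) and, where comparative, descriptive (10.8).

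What the reply does not remove is that the list is closed, the two diseases are not named, and no step is described that would reveal an omission.

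**Conclusion.** The point holds as a conditional gap in how the primary endpoint is derived. Under Table 4 as written, a subject whose only lung history is coded to a term outside the list scores 0 on this item, and the plan does not show that emphysema and chronic bronchitis are inside it.

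The loss is 0.024 on the index with complete questionnaires, and up to 0.032 with 10 items missing. It alters the category only for subjects within one point above a cut-off. The number of such subjects is unknown and may be zero. Any effect falls on the frailty distribution and on who belongs to which subgroup, not on the comparison between vaccine and placebo.

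This rests on one assumption that a dictionary check can settle, namely that neither disease is a member of the three queries in MedDRA version 18, and on some subjects having been coded to those terms alone. The change is worth making because it costs little and does nothing if the terms are already captured.

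**What to change.** 1. In the Chronic Lung Disease row of SAP Table 4, add the MedDRA version 18 preferred terms for emphysema and chronic bronchitis. If a look-up shows that a listed query already contains them, a footnote saying so is enough.
2. Before the final analysis, list all coded respiratory medical-history terms that the row does not capture, and add any that is a chronic lung disease. Decide this without sight of vaccination group or HZ outcome, since those data already exist.

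The cost is a look-up, at most a few extra terms, one listing and a rerun of the index derivation if it has already been programmed. The documents do not say whether the search has been run. No new data are needed.
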